PwMS will be randomly assigned to one of four groups: ctDCS and gait training, sham and gait training, ctDCS and balance training, or sham and balance training (n = 12 per group). Each subject will attend a total of 14 experimental sessions. Session 1 will be a familiarization session and will last approximately 45 minutes. The duration of the baseline (Session 2) and 24-hour post-intervention session (Session 12) will be approximately 3 hours. The ctDCS and gait training sessions (Sessions 3 – 11) will last approximately 1.5 hours. Finally, the two- and four-week post-intervention sessions (Sessions 13 and 14, respectively) will be approximately one hour. During the initial session, subjects will be consented and complete strength testing to objectively determine the more-affected leg. Additionally, during Session 1 subjects will become familiar with treadmill walking and determine a self-selected speed for subsequent testing sessions. During the baseline session (Session 2), subjects will 1) complete the Fatigue Severity Scale (FSS)63, 2) undergo a whole-body FDG/PET scan after 20 minutes of treadmill walking at their self-selected speed, 3) perform the Functional Gait Assessment (FGA), 4) Timed 25-Foot Walk Test (T25WT), 5) Berg Balance Scale (BBS), 6) static posturography, and 7) the 6-minute walk test (6MWT) while wearing inertial sensors. The following 9 days will include 20 minutes of either 4 mA or sham ctDCS, 10 minutes of rest to allow for peak stimulation effects, and then approximately 40 minutes of gait or balance training. Session 12 will consist of the same testing battery as Session 2. Long term effects (2- and 4-weeks post-intervention) will be assessed with the 1) FSS questionnaire, 2) FGA, 3) T25FW, 4) BBS, 5) static posturography, and 6) the 6MWT during Sessions 13 and 14.

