A stimulation (sham vs. 4 mA) by training (balance vs. gait) by time (24 hours, 2 weeks, and 4 weeks) ANCOVA with baseline measurements as covariates will be conducted on each outcome variable (e.g., distance walked on the 6MWT and FGA score) to compare the short- and long-term effects of gait and balance training combined with ctDCS. Levene's test and normality tests (QQ plots, Shapiro Wilk test, and histograms) will be used to test the statistical assumptions. Post-hoc testing (paired and unpaired t-tests) and effect sizes (Cohen's d) will be calculated to clarify significant main or interaction effects. Significance will be accepted at $p < 0.05$ and adjusted with a Bonferroni correction. Statistical analyses will be performed using SPSS 27 (IBM Corp, Armonk, NY, USA).

XI.2*Provide the rationale or power analysis to support the number of subjects proposed to complete this study.*

We used effect sizes (Cohen's $d = 2.08$ and 1.37 , respectively) from Pilloni et al. 202060 and Hebert et al. 201146 to calculate the required sample size. With a significance fixed at $p = 0.05$ and 80% power, we will require 40 total subjects ($n = 10$ in each group) to properly power the hypothesis test for a statistically significant change. Based on this calculation and the assumption of a standard drop out rate of approximately 20%, we propose to recruit 48 total subjects ($n = 12$ in each group).

XII. Future Research

XII.1 *Do you wish to keep any information about subjects involved with this research project so that members of the current research team may contact them in the future for your own research projects?*
Yes

XII.2 *Do you wish to keep any information about subjects involved with this research project so that other researchers may contact them for future research?*
Yes

XII.3 *List the data or information you will keep:*
Contact information and outcome of the phone questionnaire.

XII.4 *Does this project involve storing any data, tissues or specimens for future research?*
Yes – contribution for future use is mandatory for participation in the study

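### XI.1 does not say at what baseline value the time effect is tested; if raw baselines are entered in SPSS GLM Repeated Measures, that value is zero

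*Combined protocol and SAP*

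**What the plan says.** Section XI.1 specifies one model for every outcome: stimulation (two levels) by training (two levels) "by time (24 hours, 2 weeks, and 4 weeks) ANCOVA with baseline measurements as covariates will be conducted on each outcome variable". Its purpose is "to compare the short- and long-term effects of gait and balance training combined with ctDCS". Post-hoc t-tests and Cohen's d "will be calculated to clarify significant main or interaction effects", so a significant time main effect is one of the results that open the post-hoc comparisons. Significance is set at 0.05, "adjusted with a Bonferroni correction". On software, the plan says only "Statistical analyses will be performed using SPSS 27".

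Section VII.E.6 supplies the later visits: "Long term effects (2- and 4-weeks post-intervention) will be assessed" with the fatigue scale, FGA, T25FW, BBS, posturography and 6MWT. PET is done only in Sessions 2 and 12, so it has no three-visit time effect.

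XI.1 does not name the SPSS procedure. It does not say whether baseline is raw or centred, whether baseline by time is in the model, or at what baseline value the visits are compared. VII.B.11 answers that there is no separate written protocol, so the documents point to nowhere else where this is settled.

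**The concern.** A factorial ANCOVA over three visits, checked with Levene's test and run in SPSS, reads most naturally as GLM Repeated Measures. That procedure adds the product of each covariate with the within-subject factor, which amounts to a separate baseline slope at each visit. The time main effect then compares the three visit intercepts. With baseline entered as measured, an intercept is the predicted outcome for someone whose baseline is zero.

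Nobody enrolled is near that value. VI.13 requires participants to walk on a treadmill for at least 20 minutes, which rules out 0 m on the 6MWT and 0 s on the T25FW. An FGA of 0 means severe impairment on all ten items, and a BBS of 0 is equally remote in practice.

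What is at stake is the overall statement about whether performance holds from 24 hours to 4 weeks. An extrapolated test can miss a real decline. If the baseline slope changes between visits, it can also signal a change that has not occurred at the average baseline.

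**Working it through.** **Inputs from the documents.** Three post-intervention visits and a 2 x 2 between-subject design (XI.1); 40 evaluable participants, 10 per group (XI.2). The plan gives no figure for the time test. Its sample size is a between-group figure and can be reproduced: d = 1.37 at two-sided 0.05 needs 10 per group (power 82.6%), and d = 2.08 needs 5.

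**Assumed inputs.** The documents give no mean, SD or correlation for any outcome. Main case for the 6MWT: mean 400 m, SD 100 m at every visit, baseline to follow-up correlation 0.85, correlation among follow-ups 0.90, linear decline of 25 m from 24 hours to 4 weeks. Tests are at 0.05 without Bonferroni adjustment.

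**Step 1: loss of precision.** With baseline by time in the model, the standard error of a visit contrast at baseline 0, relative to the mean baseline, is about sqrt(1 + N/((N-1) x CV^2)), where CV is the baseline SD divided by its mean. With N = 40:

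| Baseline CV | SE ratio |
|---|---|
| 0.10 | 10.2 |
| 0.20 | 5.2 |
| 0.25 | 4.2 |
| 0.30 | 3.5 |
| 0.40 | 2.7 |
| 0.50 | 2.3 |

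In the main case (CV 0.25), the SD of the 24-hour to 4-week difference is 100 x sqrt(2 x (1 - 0.90)) = 44.7 m. Its SE at the mean baseline is 44.7/sqrt(40) = 7.1 m, so a 25 m decline is about 3.5 standard errors. At baseline 0 the SE is 7.1 x 4.17 = 29.5 m, and the same decline is about 0.85 standard errors.

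**Step 2: power with equal slopes.** In 6,000 simulated trials of the main case, the time test rejects in about 88% with a centred baseline and 10% with a raw one. With no decline, both reject in about 5%.

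**Step 3: slopes that change.** Let the means stay at 400 m and the baseline correlations be 0.90, 0.85 and 0.80. With equal SDs the slopes equal the correlations. The prediction at baseline 0 is 400 - 0.90 x 400 = 40 m at 24 hours and 400 - 0.80 x 400 = 80 m at 4 weeks. That is a 40 m difference which does not exist at the mean. The raw test rejects in about 18% of trials and the centred test in about 5%.

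**Step 4: other assumptions.** Each row has 10 per group and 4,000 runs.

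| Assumed case | Raw | Centred |
|---|---|---|
| 6MWT mean 450, SD 100, residual SD 40, residual correlation 0.6; decline 0/15/30 m | 14% | 99.8% |
| Same, no mean change, slopes 0.95/0.85/0.75 | 80% | 8% |
| FGA mean 22, SD 4.5; decline 0/1/2 points | 20% | 100% |
| BBS mean 49, SD 5; decline 0/0.8/1.5 points | 7% | 99.9% |

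**Step 5: what does not move.** In these simulations the F values for time by stimulation, time by training and the three-way term were the same raw and centred, to within 1e-12. The between-group tests are also unchanged, because baseline does not interact with group in the model.

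**The case against.** The strongest reply is that the documents do not commit this error. XI.1 says neither that baseline is raw nor which procedure is used. A mixed model without baseline by time, or a centred covariate, fits the same sentence and has no problem. The behaviour of GLM Repeated Measures is software knowledge, not something the plan states. This stands: the point is an unspecified detail whose likely default works badly, and it must be put conditionally.

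A reader might also infer that the planned comparison of short- and long-term treatment effects is invalid. The documents do not support that. XI.1 does not assign the comparison to the time main effect. Whether a ctDCS or training effect differs between visits is tested by the interactions with time, which do not depend on centring. The time main effect averages over sham and active arms and cannot isolate persistence of a ctDCS benefit. The hypotheses in I.5 are between-group contrasts and are untouched.

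Nor can the raw p-value be called meaningless in general. With equal slopes it keeps its 5% error rate and only loses power. Excess false positives need slopes that differ by visit, and nothing in the documents bears on that.

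Finally, the sizes are driven by assumptions. An outcome with a baseline CV of 100%, which some sway measures might approach, would have an SE ratio of only about sqrt(1 + 1) = 1.4. A Bonferroni-adjusted threshold would lower every rejection rate above. The paired post-hoc t-tests do not depend on centring; only the trigger for them does. What survives is that the likely default gives a poor time test and that avoiding it is almost free.

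**Conclusion.** The point holds as a conditional gap in specification. If XI.1 is run as GLM Repeated Measures with baseline as measured, the time main effect is tested at a baseline of zero, outside the enrolled population, and cannot be read as change at the average baseline. Under the assumed main 6MWT case, power for a 25 m decline falls from about 88% to 10%. With the assumed falling correlations, rejection without any change in means rises from about 5% to 18%. Other assumed values move these figures widely, but in the cases examined with a real decline or changing slopes the raw test did worse. The consequence is confined to the overall change from 24 hours to 4 weeks on outcomes measured at all three visits, and to the post-hoc tests that this result opens. It is worth correcting before analysis, but it does not threaten the trial's treatment comparisons.

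**What to change.** Name the SPSS procedure in XI.1 and add one sentence: each baseline covariate is grand-mean-centred before entry, so that time is tested at the mean baseline. The cost is one computed variable per outcome. No group test or group-by-time test changes, and no data or participants are added.

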STRENGTH TESTING: Strength testing will be performed in a sitting position on an isokinetic dynamometer (CSMi, Stoughton, MA, USA). The subject will be secured with Velcro bands to help isolate the knee joint and the range of motion will be set between 100° and 0° of flexion. Strength testing will begin with a 15-repetition warm up of the knee extensors and flexors at 60/s (concentric/concentric). After a 30 second rest, 3 sets of 1 maximal effort isometric contraction of the knee extensors and flexors will be performed at 65° and 30°, respectively, with 30 s of rest between each set. Isokinetic strength testing will consist of 3 sets of 1 maximal effort knee extension and flexion (60/s, concentric/concentric) with 30 s of rest between each set. All testing will be completed on both legs and the largest torque obtained from a given muscle group in any of the strength testing conditions (isometric or isokinetic) will be used to verify leg dominance.

FUNCTIONAL GAIT ASSESSMENT (FGA): The FGA is a valid measure of walking balance and consists of 10 challenging tasks, such as walking with a narrow base of support (i.e., tandem stance), walking backwards, and walking with eyes closed. Each item is graded from 0 (severe impairment) to 3 (normal performance), with a maximum score of 3068. The minimal clinical important difference (MCID) for the FGA has not been established in PwMS. However, in other neurological populations, a MCID of 4-6 points has been suggested.

TIMED 25-FOOT WALK TEST (T25FW): The T25FW test resembles relevant daily life situations, such as walking across a signaled intersection, is well-established and has very good psychometric properties. In a cordoned-off hallway, subjects will be instructed to walk as fast as possible between two points separated by 25 feet during two separate trials65. The shortest time it takes to complete the 25-foot walk will be the main outcome variable. Gait characteristics will also be recorded using six inertial sensors (OPAL inertial motion units [APDM, Portland, OR, USA]) located on the chest/sternum, each wrist and foot, and on the lower back (5th lumbar). A 20% decrease in the time it takes to complete the T25FW has been established as a significant change in PwMS.

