BERG BALANCE SCALE (BBS): The BBS is a valid and reliable assessment of balance during static (e.g., standing with eyes closed) and dynamic (e.g., completing a 360-degree turn) conditions. A cut-off score of 44 has been established as a criterion to identify PwMS with a high fall risk. Furthermore, it has been shown that the minimal clinically important difference (MCID) for the BBS in PwMS is 3 points.

STATIC POSTUROGRAPHY: Static posturography will be examined on a Balance Plate (Balance Tracking Systems, San Diego, CA, USA). Participants will stand on both firm (i.e., the force plate) and compliant (i.e., a 6 cm Airex Balance Pad Elite 76 [Airex AG, Sins, Switzerland] placed on the force plate) surfaces with their eyes open and with their eyes closed for one minute each. The addition of a foam pad increases the difficulty of maintaining balance by changing foot pressure distribution and decreases the input of cutaneous mechanoreceptors and joint receptors. The center of pressure average movement velocity in the anterior-posterior and medial-lateral directions and the area of an ellipse that encapsulates 95% of the 2D area explored will be the primary outcomes.

6-MINUTE WALK TEST (6MWT): The 6MWT is considered the “gold standard” for a long walking test in interventional research. The subjects will be led to a cordoned-off hallway to perform the walk. Subjects will be instructed to walk as far as possible between two points separated by 30 m for 6 min. Gait characteristics and distance walked will be calculated and recorded using six inertial sensors (OPAL inertial motion units [APDM, Portland, OR, USA]) located on the chest/sternum, each wrist and foot, and on the lower back (5th lumbar).

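### No trial-level primary outcome is named and the Bonferroni family is undefined, so neither the error rate across outcomes nor the stated 80% power is tied to an identified test

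*Combined protocol and SAP*

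**What the plan says.** - **Hypotheses (I.5).** Gait, balance and glucose-uptake symmetry are all expected to improve more with active stimulation than with sham, within each training type. The largest gain is expected with gait training plus stimulation. None of the three domains is ranked first.
- **Outcomes (VII.E.6).** The follow-up battery is FSS, FGA, T25FW, BBS, static posturography and 6MWT. For the T25FW: "The shortest time it takes to complete the 25-foot walk will be the main outcome variable". For posturography, two sway velocities and one ellipse area "will be the primary outcomes", recorded on two surfaces with eyes open and eyes closed. Inertial sensors add gait characteristics whose number is not given.
- **Analysis (XI.1).** The three-factor ANCOVA with baseline as covariate "will be conducted on each outcome variable (e.g., distance walked on the 6MWT and FGA score", so the list is open. The only multiplicity rule is that significance at p < 0.05 is "adjusted with a Bonferroni correction". The divisor is not stated: it could count outcomes, model effects, visits or post-hoc pairs.
- **Sample size (XI.2).** "We used effect sizes (Cohen's $d = 2.08$ and 1.37 , respectively" refers to two published studies; the outcome and contrast behind each value are not given. "With a significance fixed at $p = 0.05$ and 80% power, we will require 40 total subjects", that is 10 per group, with 48 recruited.

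**The concern.** A Bonferroni rule protects only the family that it is applied to, and this plan leaves that choice open until the results are known. If the correction covers only follow-up comparisons within an outcome, each outcome is in effect tested at 5%, and significance on any one of them could be presented as support for the hypothesis. If it covers the outcomes, the threshold is much stricter than the one used to size the trial. Because the effect sizes belong to no named outcome or contrast, a reader cannot tell which test has the stated 80% power. At stake is what the trial may conclude from a mixed set of results, which is the likely pattern with this many related measures.

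**Working it through.** **Inputs.** From XI.2: d = 1.37 and 2.08, alpha 0.05, power 80%, 10 evaluable per group, four groups. From VII.E.6: the outcome list. Assumed, because the documents do not say: two-sided tests, and the correlation between outcomes (range shown).

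**1. Reproducing the plan's n.** For a two-sample t-test with n per group, the noncentrality is d × √(n/2) on 2n − 2 degrees of freedom.
- d = 1.37, n = 10: 1.37 × √5 = 3.06; critical t (18 df) = 2.10; power 82.6%.
- n = 9 gives 77.9%, so 10 is the smallest n reaching 80%.
- d = 2.08 would need only 5 per group, and a one-sided test at d = 1.37 only 8.

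The stated n therefore matches one pairwise 10-vs-10 comparison at d = 1.37 and an unadjusted two-sided 0.05.

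**2. Counting outcomes.** Named scores: FSS, FGA, T25FW, BBS, 6MWT = 5. Posturography: 3 measures, or 3 × 2 surfaces × 2 eye conditions = 12 if each condition is analysed separately. The total is 5 + 3 = 8 or 5 + 12 = 17, before sensor variables. FSS is a fatigue questionnaire; without it, 17 becomes 16. FDG outcomes are not counted.

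**3. If Bonferroni stays within an outcome.** Take one stimulation test per outcome at 0.05. Under independence the chance of at least one false positive is 1 − 0.95^m: 1 − 0.95^5 = 22.6% and 1 − 0.95^17 = 58.2%. With an assumed common correlation (simulated equicorrelated normal statistics):

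| Assumed correlation | 5 outcomes | 17 outcomes |
|---|---|---|
| 0 | 23% | 58% |
| 0.3 | 21% | 49% |
| 0.5 | 18% | 39% |
| 0.8 | 13% | 21% |
| 0.9 | 10% | 15% |

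**4. If Bonferroni covers the outcomes.** Alpha is 0.05/5 = 0.01 or 0.05/17 = 0.00294. Power by noncentral t, with no gain from baseline adjustment:

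| Contrast | 0.05 | 0.05/5 | 0.05/17 |
|---|---|---|---|
| Pairwise 10 vs 10, d = 1.37 | 83% | 58% | 39% |
| Pooled 20 vs 20, d = 1.37 | 99% | 94% | 86% |
| Pairwise 10 vs 10, d = 2.08 | 99% | 95% | 86% |

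For the pairwise comparison at d = 1.37 and 0.05/17, power is 52% even if all 12 per group complete. Reaching 80% takes 18 per group, 4 × 18 = 72 evaluable.

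**5. Baseline adjustment.** If baseline and follow-up correlate at ρ, the effective effect size is d/√(1 − ρ²). For the pairwise comparison at d = 1.37 and 0.05/17, power is 54% to 63% at ρ = 0.5 and 77% to 85% at ρ = 0.7, depending on the error degrees of freedom. The documents give no ρ.

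**The case against.** A reader might infer that the plan must fail one way or the other: the 5% error rate is lost or the 80% power is. The documents do not support that. The stimulation main effect in the planned ANCOVA pools over training type, so it compares 20 with 20. At d = 1.37 it keeps about 86% power under full Bonferroni over 17 outcomes, as does a pairwise contrast at d = 2.08. Strong baseline correlation would also recover much of the loss. This objection stands, and it confines the power shortfall to the pairwise comparison at d = 1.37. It does not clear the plan: XI.2 does not say that its 80% refers to the pooled effect, its n matches the pairwise calculation, and the comparisons in I.5 are largely pairwise. At a divisor of 51 (17 outcomes × 3 visits) even the pooled effect falls to 77%.

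Other points also stand in part. The count of 17 is constructed: VII.E.6 lists three posturography measures and does not say how the four conditions will be analysed. Independence is implausible for related gait and balance measures, so 58% is an upper figure for one test on each of 17 outcomes. The labels main and primary in VII.E.6 pick the readout of each test; they are not rival trial-level primaries. The plan does not call itself confirmatory, although it does state directional hypotheses and speaks of 10 per group as enough "40 total subjects ($n = 10$ in each group) to properly power the hypothesis test for a statistically significant change". Finally, part of the application between the reference list in I.7 and item V.4 was not available, so a primary named there cannot be excluded. Sections XI.1 and XI.2 refer to none.

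**Conclusion.** The point holds in a limited form. The available sections name no trial-level primary outcome, the Bonferroni family is undefined, and the sample size rests on an unadjusted 0.05 and effect sizes tied to no named outcome or contrast.

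If the correction is confined to post-hoc pairs, error across outcomes exceeds 5% at every correlation examined, and reaches two to nearly five times 5% even when only the five named scores are counted. If the correction spans outcomes, the comparison that reproduces the stated n falls well short of 80% unless baseline correlation is high.

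It does not follow that every contrast is underpowered, or that no reading of the plan can control error and keep power: the pooled stimulation effect can do both at a divisor of 17, provided d = 1.37 applies to it. The figures rest on two-sided testing, one stimulation test per outcome and equal correlation between outcomes. This is more than a missing detail, because the choice left open decides what the trial can claim.

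**What to change.** Before unblinding, and before any outcome is tabulated by arm:

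1. Name one primary outcome, time point and contrast, and test it once at 0.05. One example is baseline-adjusted 6MWT distance at 24 hours, stimulation effect pooled over training type.
2. Rewrite XI.2 so that the effect size, sidedness and power refer to that test. With 10 evaluable per group and d = 1.37, a pairwise primary has about 83% power and a pooled one about 99%, if that effect size is justified for the chosen outcome.
3. Label all other outcomes, visits and interactions secondary. Either apply Bonferroni or Holm over a family that is listed in full, including how the four stance conditions and the sensor variables enter, or report estimates with 95% confidence intervals only.

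This is a cheap improvement: it changes wording in the protocol and SAP and needs no new participants, visits or measurements. The cost is that the other outcomes lose confirmatory status.

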Many people with multiple sclerosis (PwMS) have decreased balance (1,2) and postural control(3), gait deficits(4), and a high frequency of falls(5). High fall rates and mobility impairments pose a significant risk to the independence and quality of life of PwMS(8,9). Therefore, effective interventions to improve gait, balance and postural control are urgently needed to decrease the frequency of falls in PwMS. Gait and balance training has been demonstrated to significantly improve postural control and gait in PwMS (10,11). However, a standardized protocol for balance interventions has not been established. However, the cumulative evidence shows that only small improvements in walking ability are associated with exercise training short-term and the long-term effects are ambiguous (13). One possible treatment modality to amplify the effects of gait balance training is transcranial direct current stimulation (tDCS), a non-invasive means to increase cortical excitability and potentially prime the brain for task specific learning(14). The cerebellum plays a vital role in balance and posture and may be an important target structure for tDCS studies seeking to improve gait and balance (14-17). Studies have shown that anodal cerebellar tDCS is effective in improving balance control in older adults with high fall risk(18) and patients with chronic stroke(19). However, the most effective tDCS intensity and the duration of the effects on gait balance control has not been established(20,21).

I.7***Literature cited / references (if attaching a grant or protocol enter N/A).***

1. Martin, C. L., Phillips, B. A., Kilpatrick, T. J. et al. Gait and balance impairment in early multiple sclerosis in the absence of clinical disability. *Mult Scler* 12, 620-628, doi:10.1177/1352458506070658 (2006).
3. Cameron, M. H. & Lord, S. Postural control in multiple sclerosis: implications for fall prevention. *Curr Neurol Neurosci Rep* 10, 407-412, doi:10.1007/s11910-010-0128-0 (2010).

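### The analysis sets out to compare short- and long-term tDCS effects but pre-specifies no 4 mA versus sham estimate at any visit; visit comparisons are post-hoc t-tests that follow a significant omnibus result and drop the baseline adjustment

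*Combined protocol and SAP*

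**What the plan says.** Section XI.1 specifies, for each outcome, "A stimulation (sham vs. 4 mA) by training (balance vs. gait) by time (24 hours, 2 weeks, and 4 weeks) ANCOVA" with baseline as covariate. Its stated purpose is "to compare the short- and long-term effects of gait and balance training combined with ctDCS".

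The follow-up rule in the same section is: "Post-hoc testing (paired and unpaired t-tests) and effect sizes (Cohen's d") "will be calculated to clarify significant main or interaction effects". On multiplicity it says: "Significance will be accepted at $p < 0.05$ and adjusted with a Bonferroni correction". It does not say which comparisons make up the Bonferroni family.

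Section VII.E.6 defines the long-term visits: "Long term effects (2- and 4-weeks post-intervention) will be assessed with the" functional tests and the fatigue scale at Sessions 13 and 14. The background (I.6) says of the existing literature that "the duration of the effects on gait balance control has not been established". The hypotheses in I.5 name no visit.

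The sample-size section (XI.2) works "With a significance fixed at $p = 0.05$ and 80% power" from two effect sizes, d = 2.08 and 1.37. It attaches no visit or time course to either.

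**The concern.** Short-term and long-term effects are two separate quantities: the 4 mA minus sham difference at 24 hours, and the same difference at 2 and 4 weeks. The plan never names either as something to be estimated.

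- The stimulation main effect is the mean over the three visits.
- Stimulation by time asks whether the difference changes. It does not say how large the difference is at any visit.
- The t-tests that could show this are conditional on an omnibus result, and as named they carry no baseline covariate.

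Two things are at stake. First, if stimulation is significant and stimulation by time is not, the plan requires no 4-week estimate, so a long-term claim could be made without one. Second, where visit comparisons are made, an unadjusted test gives up precision that the trial has already paid for by measuring baseline. With 10 completers planned per group, that precision matters.

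**Working it through.** **1. The plan's own figure.** A two-sided two-sample t-test at 0.05 with 80% power and d = 1.37 needs 9.43, so 10 per group, and 4 × 10 = 40. This matches XI.2. Power at 10 per group is 82.6%. With d = 2.08, 5 per group would do. The sample size is therefore that of a simple two-group comparison, with no time course in it.

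**2. What each term estimates.** Write δ1, δ2 and δ3 for the 4 mA minus sham difference at 24 hours, 2 weeks and 4 weeks.
- Main effect: (δ1 + δ2 + δ3)/3. With δ = (1.37, 0.685, 0) this is 2.055/3 = 0.685, which is not the effect at 24 hours or at 4 weeks.
- Stimulation by time tests δ1 = δ2 = δ3. It detects fading but gives no δ.

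**3. Cost of dropping the baseline covariate.** Inputs from the plan: 10 completers per group, hence 20 per stimulation arm pooled over training, and alpha 0.05 (two-sided assumed). The documents give no correlations, so I assume a common correlation r of 0.5 to 0.8 between baseline and all visits.

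The adjusted effect is d/√(1 − r²), and the noncentrality is that effect × √(20/2).
- r = 0.5, d = 0.79: adjusted 0.79/0.866 = 0.91, noncentrality 0.91 × 3.162 = 2.88; unadjusted 0.79 × 3.162 = 2.50.
- r = 0.8, d = 0.55: adjusted 0.55/0.6 = 0.92, noncentrality 2.90; unadjusted 0.55 × 3.162 = 1.74.

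**4. Simulation of the planned model.** 6,000 trials per row, δ = d × (1, 0.5, 0), every test at 0.05.

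| r | d at 24 h | 24 h adjusted | 24 h unpaired t | Main effect | Stimulation × time | Main only, interaction not |
|---|---|---|---|---|---|---|
| 0.5 | 0.79 | 79% | 69% | 46% | 58% | 19% |
| 0.7 | 0.65 | 79% | 50% | 42% | 63% | 16% |
| 0.8 | 0.55 | 78% | 39% | 42% | 64% | 15% |
| 0.5 | 1.37 | 99.8% | 99% | 89% | 97% | 2.8% |
| 0.7 | 1.37 | 100% | 99% | 96% | 99.8% | 0.2% |
| 0.8 | 1.37 | 100% | 99% | 99% | 100% | 0% |

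Dropping the covariate costs about 10 to 40 points of 24-hour power for the smaller effects, and about 1 point at d = 1.37.

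**5. Gate and Bonferroni.** The family is undefined. If it were three visits (0.05/3 = 0.0167), the adjusted 24-hour contrast for the smaller effects would have about 61% to 63% power with no gate. Requiring either omnibus test first lowers this to about 58% to 60%, so the gate itself costs about 3 points. The rest of the fall from 79% comes from the assumed divisor.

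**6. A sustained effect.** With δ = (1.37, 1.37, 1.37), the main effect is significant and the interaction is not in about 95% to 96% of trials. That is the correct result, yet the plan still calls for no 4-week estimate to go with it.

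**The case against.** The strongest defence is that the model already addresses the time course. A reader might infer that tDCS is tested only through an effect averaged over visits. The documents do not support this: stimulation is crossed with time, and significant interactions are followed up. In the fading scenarios above, stimulation by time has more power than the main effect, and it can open the visit comparisons when the average is not significant. This part of the defence stands in full.

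A reader might also take the 15% to 19% in the last column as the rate at which a fading effect would be declared lasting. That does not follow. Nothing in XI.1 says that a non-significant interaction establishes a uniform effect, or that visit comparisons are barred after a significant main effect; follow-up is allowed for either. If those trials do go on to a 4-week contrast at 0.05/3, the share of all trials in which the main effect alone is significant and that contrast is too is about 0.6% to 0.8%. At d = 1.37 the main-effect-only path occurs in 0 to 3% of trials. Nor can the fall from about 79% to about 60% be charged to the gate, because most of it is the divisor of three, which the plan does not state.

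Finally, the follow-up might in practice be run on baseline-adjusted means. That would remove the loss in step 3, but the plan names paired and unpaired t-tests, so it should say so.

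The defence does not supply a planned estimate at any visit, an interval, or a stated basis for a long-term claim.

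**Conclusion.** The point holds as a gap in estimation and reporting. The plan's purpose calls for the 4 mA versus sham difference at named visits. The plan produces such differences only after a significant omnibus test, by tests that as written ignore baseline, and under an undefined multiplicity family.

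The one loss that can be sized without guessing the Bonferroni family or the follow-up rule is the lost baseline adjustment: about 79% down to about 40% to 69% at 24 hours. It rests on assumed correlations of 0.5 to 0.8, 10 completers per group, pooling over training, and effects (d about 0.55 to 0.79) well below the planning value. At d = 1.37 either omnibus test passes in about 99.7% of trials or more and the unadjusted 24-hour test has about 99% power, so the losses are small. No inflated error rate has been shown. It is a modest change, worth making because it costs almost nothing.

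**What to change.** In XI.1, from the same baseline-adjusted model:

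- Pre-specify the 4 mA minus sham difference at 24 hours, 2 weeks and 4 weeks for each outcome measured at those visits, each with a 95% confidence interval and reported whatever the omnibus tests show. These replace the unpaired t-tests for visit comparisons between stimulation arms.
- State that a short-term claim rests on the 24-hour contrast and a long-term claim on the 2- and 4-week contrasts, never on a non-significant interaction.
- State the Bonferroni family for these contrasts.
- Keep the averaged main effect and the stimulation-by-time test. With a fully sustained effect the average is the stronger summary: 93% to 96% power, where a 24-hour contrast has about 79%.

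A fixed testing order (24 hours, then 4 weeks) is optional. It avoids splitting alpha within one outcome, but it would block a claim of a delayed effect.

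Cost: a few sentences, no new data or visits, and three more reported contrasts per outcome.
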